#### Informed Consent

All participants will be informed of the purpose of the research, including the potential benefits and risks of PMTCT/EID engagement and VL testing and, at HITSystem-implementing sites, the unique communication features of the HITSystem. The Mentor Mother will go over the informed consent with each woman and then allow her to read it over on her own. Mentor mothers will explain that all participants have the right to discontinue participation at any time and that women who decline study participation will access standard of care PMTCT/EID services. At HITSystem study sites, caregivers declining study participation can also choose to be tracked in the HITSystem without providing additional samples for VL tests

Prior to a request for written informed consent, women will be asked to summarize what they've been told/read to ensure comprehension. Women will then be asked if they would like to enroll by: a) providing their cell phone contact and/or tracing information from the hospital to their residence to facilitate follow up, b) allowing their and their infant's patient

information to be entered and tracked in the HITSystem (at HITSystem sites only), and c) consenting to receive research-specific VL testing at delivery. Women who are non-literate will have the option of using a thumb-print in lieu of a signature for study consent. Pregnant women under the age of 18 are eligible for inclusion in this study. Since Kenyan law allows pregnant women/mothers the same capacity to consent as an adult, young women under the age of 18 will be able to provide consent for themselves. Mentor mothers will take additional time with these young women to ensure comprehension, emphasizing that participation is optional and is not a requirement for receiving standard of care PMTCT/EID services for themselves or their infant.

The contact number of the Study Coordinator and in-country PI will be provided to all who agree to participate. Participants will be encouraged to call this number if they have questions about their participation in the study. IRB approval will be sought from KEMRI and the University of Kansas Medical Center.

#### **9.0 Expected application of the results**

Findings from this study will make an important contribution to PMTCT services in Kenya and other comparable low resource countries and will contribute to the limited data regarding the implementation of eHealth strategies and viral suppression in this context. As Kenyan and global recommendations move toward eHealth and more stringent viral load monitoring strategies, it is critical to assess the performance and cost-effectiveness of these methods in resource-constrained settings. This data will provide evidence for Ministries of Health and other organizations to consider optimal mHealth strategies to meet the global goal of eliminating new HIV infections in children through PMTCT services. We will work with participating counties throughout the study period to develop sustainability plans beyond the course of the study. If efficacious, we will work with potential funders to facilitate the roll out of HITSystem 2.1 at health facilities throughout Kenya.

## 11.0 Budget

Please note, all budgetary information is subject to change based on final staffing decisions and final award amount. All amounts are shown in U.S. dollars (USD, \$)

Below the combined estimated study budget for years 1 through 5 and total across all five years are outlined. These funds will be distributed among the four partnering institutions (KUMC, GHI, KEMRI, CMH).

| Overview                                       | 01 Year        | 02 Year        | 03 Year        | 04 Year        | 05 Year        | 01-05 Years      |
|--|----------------|----------------|----------------|----------------|----------------|------------------|
| Salaries                                       | 268,822        | 270,424        | 275,831        | 281,351        | 266,898        | 1,363,326        |
| Fringes  | 86,094         | 82,836         | 84,489         | 86,182         | 83,376         | 422,977          |
| Consultants                                    | 12,000         | 2,500          | 2,000          | 1,500          | 6,500          | 24,500           |
| Equipment                                      | 0              | 0              | 0              | 0              | 0              | 0                |
| Materials and Supplies                         |                |                |                |                |                |                  |
| Training                                       | 8,300          | 0              | 0              | 0              | 0              | 8,300            |
| Printing                                       | 1,100          | 2,900          | 3,000          | 3,000          | 2,900          | 12,900           |
| Communication                                  | 5,200          | 10,200         | 10,200         | 10,200         | 10,100         | 45,900           |
| HITSsystem usage costs (licensing/airtime)     | 7,800          | 9,000          | 9,000          | 9,000          | 9,000          | 43,800           |
| Staff support (MM salary, SC health insurance) | 36,720         | 69,840         | 69,840         | 69,840         | 36,720         | 282,960          |
| VL testing costs                               | 15,720         | 14,690         | 10,190         | 1,440          | 0              | 42,040           |
| Patient tracing                                | 4,320          | 8,640          | 8,640          | 6,480          | 0              | 28,080           |
| Participant Remuneration                       | 3,600          | 0              | 0              | 2,100          | 0              | 5,700            |
| Dissemination meetings                         | 0              | 0              | 0              | 0              | 6,000          | 6,000            |
| Travel   | 54,000         | 34,000         | 34,000         | 34,000         | 44,000         | 200,000          |
| Publications                                   | 2,500          | 2,500          | 0              | 2,500          | 18,000         | 25,500           |
| Subtotal Direct Costs                          | 506,176        | 507,530        | 507,190        | 507,593        | 483,494        | 2,511,983        |
| Consortium/Contractual F&A                     | 40,543         | 41,847         | 41,971         | 41,677         | 36,052         | 202,090          |
| Indirect                                       | 168,108        | 113,945        | 114,464        | 117,623        | 136,352        | 650,492          |
| Total costs                             | 714,827 | 663,322 | 663,625 | 666,893 | 655,898 | 3,364,565 |

By institution, the estimated yearly breakdown of budget is outlined below.

|                                  | Country | 01 Year        | 02 Year        | 03 Year        | 04 Year        | 05 Year        | 05 Years         |
|----------------------------------|---------|----------------|----------------|----------------|----------------|----------------|------------------|
| Kenya Medical Research Institute | Kenya   | 42,033         | 43,148         | 43,794         | 44,456         | 42,260         | 215,691          |
| Global Health Innovations        | Kenya   | 206,547        | 241,019        | 238,173        | 230,633        | 166,723        | 1,083,095        |
| Univ Kansas Medical Center       | USA     | 410,292        | 328,935        | 330,434        | 339,553        | 393,620        | 1,802,834        |
| Children's Mercy Hospital        | USA     | 55,955         | 50,220         | 51,224         | 52,251         | 53,295         | 262,945          |
| Total                     |         | 714,827 | 663,322 | 663,625 | 666,893 | 655,898 | 3,364,565 |

## 12.0 Budget justification

The budgeted salaries will be used to support PI and Co-I from each partnering institution including [name], [name], [name], [name], [name], [name], [name], and [name]. Salaries will also cover support staff including US-based study manager and research associate and Kenya-based study coordinators (3), research assistants (2), and finance manager. Fringe benefits were calculated from each institution's established fringe rate.

Money budgeted for consultants will support HITSsystem refinement and cost-effectiveness analysis guidance.

Money budgeted for supplies will support purchase of items and services necessary to complete the scope of the study. These items include communication, printing, computers/modems/airtime/licensing for HITSystem use, VL testing support, clinical staff support, participant remuneration, health insurance, and participant tracking funds.

Money budgeted for travel will support US-based personnel travel to/from Kenya, as well as study staff (US- and Kenya-based) travel within Kenya.

Money budgeted in the “other” category will be used to pay publishing/conference fees to ensure a wide dissemination of findings within Kenya and at international venues.

#### **1. Appendix I: Informed consent documents**

Please note, the participant (intervention and control) informed consent documents will be available in English, Swahili, and Luo. The provider informed consent document will be available only in English.

### 3. Appendix II. Data collection materials

Please note, the provider interview and facility assessment form will be available in English only. All other data collection materials will be available in English, Swahili and Luo.

#### English translations

#### Appendix IIA. Enrollment Survey

##### *For interviewer to fill out:*

Study ID: \_\_\_\_\_

Date of interview \_\_\_\_\_

Interviewer initials \_\_\_\_\_

##### Mother Demographics

1. Mothers DOB: \_\_\_\_\_
2. Mother phone number: \_\_\_\_\_
3. Mother tracing information: \_\_\_\_\_
4. Date of enrollment in PMTCT services: \_\_\_\_\_
5. Estimated delivery date (EDD) \_\_\_\_\_
6. Date initiated HAART \_\_\_\_\_
7. What is your **highest level of education**?
  - a. No school
  - b. Partial primary
  - c. Completed primary
  - d. Partial secondary
  - e. Completed secondary
  - f. University/college
8. Who have you **disclosed your HIV status to**?
  - a. No one
  - b. Partner/husband
  - c. 1 or more family
  - d. 1 or more friends
  - e. 1 or more parent
9. How do you access a mobile phone?
  - a. Own phone
  - b. Shared, with someone who knows HIV status
  - c. Shared, with someone who doesn't know HIV status
  - d. Borrow phone when needed
  - e. No mobile phone access
10. Time to hospital (minutes) \_\_\_\_\_
11. Expense to hospital (roundtrip, KES) \_\_\_\_\_
12. What is your **relationship status**?
  - a. Single
  - b. Married
  - c. Unmarried, but in a relationship
  - d. Separated
  - e. Divorced
  - f. Widowed
  - g. Other, specify \_\_\_\_\_
13. What is your **living situation**?
  - a. No current partner
  - b. Live separate from partner
  - c. Live with current partner
14. How many living children do you have?
  - a. Biological \_\_\_\_\_

b. Non-biological\_\_\_\_\_

15. Have you ever been through PMTCT and/or EID services before? .....Y / N

#### Partner support & Financial Control

16. What is your partner's HIV status?

- a. HIV+
- b. HIV –
- c. Unknown
- d. No current partner

17. How did your partner react to the news of your pregnancy?

- a. Happy
- b. Neutral
- c. Unhappy
- d. Don't know
- e. No current partner

18. Who usually makes the final decision regarding how money is spent in your household?

- a. My partner, always
- b. My partner more often than me
- c. My partner and me equally
- d. Me more often than my partner
- e. Me, always.
- f. No current partner

19. Average weekly household income

- a. Less than 500 KES
- b. 500-750 KES
- c. 750-1,000 KES
- d. 1,000-2,500 KES
- e. >2,500 KES

20. I worry that I will not have enough money to reach the hospital for my own or my child's care?

- a. Strongly agree
- b. Agree
- c. Disagree
- d. Strongly Disagree

#### Partner Support

21. How important is it to you that your male partner supports you in each of the following ways?

|  | Not important at all | Not very important | Somewhat important | Very important | N/A, no partner |
|--|----------------------|--------------------|--------------------|----------------|-----------------|
| 21a. Attend your PMTCT appointments with you?  |                      |                    |                    |                |                 |
| 21b. Provide money for transport to the hospital?  |                      |                    |                    |                |                 |
| 21c. Give you advice on remaining healthy while pregnant?                                |                      |                    |                    |                |                 |
| 21d. Help you with household responsibilities so that you can rest?                      |                      |                    |                    |                |                 |
| 21e. Help you with household responsibilities so that you can attend PMTCT appointments? |                      |                    |                    |                |                 |
| 21f. Remind you to take your medication?   |                      |                    |                    |                |                 |
| 21g. Remind you of the importance of following doctor's instructions?                    |                      |                    |                    |                |                 |
| 21h. Provided money to purchase medication or vitamins?                                  |                      |                    |                    |                |                 |
| 21i. Attend the delivery?  |                      |                    |                    |                |                 |
| 21j. Provide encouragement   |                      |                    |                    |                |                 |

22. In what ways do you expect your male partner to support you during pregnancy?

|  | Do not expect | Unsure | Expect | N/A – no partner |
|--|---------------|--------|--------|------------------|
| 22a. Attend your PMTCT appointments with you?  |               |        |        |                  |
| 22b. Provide money for transport to the hospital?  |               |        |        |                  |
| 22c. Give you advice on remaining healthy while pregnant?                                |               |        |        |                  |
| 22d. Help you with household responsibilities so that you can rest?                      |               |        |        |                  |
| 22e. Help you with household responsibilities so that you can attend PMTCT appointments? |               |        |        |                  |
| 22f. Remind you to take your medication?   |               |        |        |                  |
| 22g. Remind you of the importance of following doctor's instructions?                    |               |        |        |                  |
| 22h. Provided money to purchase medication or vitamins?                                  |               |        |        |                  |
| 22i. Attend the delivery?  |               |        |        |                  |
| 22j. Provide encouragement   |               |        |        |                  |

### Depression

Please check the answer that comes closest to how you have felt IN THE PAST 7 DAYS, not just today.

23. I have looked forward with enjoyment to things
  - a. As much as I ever did
  - b. A little less than I used to
  - c. Much less than I used to
  - d. Not at all
24. I have blamed myself unnecessarily when things went wrong
  - a. Yes, often
  - b. Yes, some of the time
  - c. Not very often
  - d. No, never
25. I have felt scared or panicky for no good reason
  - a. Yes, quite a lot
  - b. Yes sometimes
  - c. No, not much
  - d. No, not at all
26. I have been so unhappy that I have been crying
  - a. Yes, most of the time
  - b. Yes, quite often
  - c. Only occasionally
  - d. No, never
27. The thought of harming myself has occurred to me
  - a. Yes, often
  - b. Sometimes
  - c. Hardly ever
  - d. Never

### Risk of Violence

For each of the following statements (27-30), choose the answer which best indicates how often each has occurred in the past 12 months

|   | Never | Rarely | Sometimes | Frequently |
|---|-------|--------|-----------|------------|
| 28. In the past 12 months, has your partner ever insulted you or made you feel bad about yourself?                          |       |        |           |            |
| 29. In the past 12 months, has your partner ever hit you, kicked you, dragged you, or beaten you up?                        |       |        |           |            |
| 30. In the past 12 months, has your partner ever hit, kicked, dragged or beaten your child?                                 |       |        |           |            |
| 31. In the past 12 months, has your partner ever physically forced you to have sexual intercourse when you did not want to? |       |        |           |            |

### PMTCT Knowledge

Please choose the best answer:

32. During pregnancy, I should receive viral load testing:
- Never, viral load testing is only conducted after delivery
  - Between 1 and 2 times.
  - At least three times.
  - Don't know
33. During pregnancy, it is recommended that HIV+ women take ART medications only if they are feeling unwell.....True / False
34. It is recommended that I attend a minimum of how many ANC appointments?
- 2
  - 3
  - 4
  - 5

#### PMTCT Motivation and self-efficacy

Please indicated the degree to which you agree or disagree with each of the following statements.

|   | Strongly Disagree | Disagree | Neutral | Agree | Strongly Agree |
|---|-------------------|----------|---------|-------|----------------|
| 35. I know I can maintain perfect adherence to my medication throughout my pregnancy , even when other people are around.    |                   |          |         |       |                |
| 36. It is very important to me that I deliver my child in a health facility, rather than at home.                                   |                   |          |         |       |                |
| 37. I am worried that I will not be able to find transport to the health facility when it is time for me to deliver my child.       |                   |          |         |       |                |
| 38. Other commitments – such as work, household duties, childcare – may prevent me from attending all of my ANC/PMTCT appointments. |                   |          |         |       |                |
| 39. Attending all ANC/PMTCT appointments is extremely important to me.  |                   |          |         |       |                |

#### COVID-related questions

Please indicated the degree to which you expect COVID-19 to impact the following events.

|   | Strongly Disagree | Disagree | Neutral | Agree | Strongly Agree |
|---|-------------------|----------|---------|-------|----------------|
| 40. I delayed coming for ANC care because of concerns related to COVID-19 exposure.   |                   |          |         |       |                |
| 41. I delayed coming to care because someone in my household or I was feeling unwell and did not want to risk exposing others to illness. |                   |          |         |       |                |
| 42. I do not want to attend the clinic as frequently for antenatal care because I am worried about COVID-19 exposure                      |                   |          |         |       |                |
| 43. I am worried that delivering in a hospital will expose me and my child to COVID-19  |                   |          |         |       |                |
| 44. Travel to and from the hospital has become more challenging (cost and/or availability of cars) as a result of COVID-19                |                   |          |         |       |                |

Thank you for your time and participation.

## Appendix IIB. Delivery survey (within 4 weeks, Intervention and Control Sites)

### For interviewer to fill out:

Study ID: \_\_\_\_\_

Date of interview \_\_\_\_\_

Interviewer initials \_\_\_\_\_

### Delivery

1. Where did you deliver your child?
  - a. Health care facility
    - i. If so, please specify which one \_\_\_\_\_
  - b. Traditional birth attendant
    - i. If so, please specify location of delivery \_\_\_\_\_
  - c. Home
  - d. Other
    - i. Please specify \_\_\_\_\_
2. Approximately how long did you labor to deliver your child?
  - a. < 2 hours
  - b. 2-5 hours
  - c. 6-12 hours
  - d. > 12 hours
3. Did you or the infant experience any complications?
  - a. yes
    - i. Please explain for mother and/or infant separately: \_\_\_\_\_  
\_\_\_\_\_
  - b. no

### Partner status & Disclosure

4. What is your **relationship status**?
  - a. Single
  - b. Married
  - c. Unmarried, but in a relationship
  - d. Separated
  - e. Divorced
  - f. Widowed
  - g. Other, specify \_\_\_\_\_
5. What is your **living situation**?
  - a. No current partner
  - b. Live separate from partner
  - c. Live with current partner
6. Is your current partner the infant's father?.....Y / N
7. Who have you **disclosed your HIV status to**? Select all that apply.
  - a. No one
  - b. Partner/husband
  - c. 1 or more family
  - d. 1 or more friends
  - e. 1 or more parent
8. What is your partner's HIV status?
  - a. HIV+
  - b. HIV –
  - c. Unknown
  - d. No current partner
9. Who usually makes the final decision regarding how money is spent in your household?
  - a. My partner, always

- b. My partner more often than me
  - c. My partner and me equally
  - d. Me more often than my partner
  - e. Me, always.
  - f. No current partner
10. Average weekly household income
- a. Less than 500 KES
  - b. 500-750 KES
  - c. 750-1,000 KES
  - d. 1,000-2,500 KES
  - e. >2,500 KES
11. I worry that I will not have enough money to reach the hospital for my own or my child's care?
- a. Strongly agree
  - b. Agree
  - c. Disagree
  - d. Strongly Disagree

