**Participant surveys:** A brief enrollment survey will collect same demographic and clinical data at control sites (without HITSystem 2.1) in addition to patient-level data regarding PMTCT information, motivation, partner status and support, HIV disclosure, depression (modified Edinburgh postnatal scale), and risk of violence (both arms, Appendix 2A). Repeated surveys after delivery and 6m postpartum (for VL sample collection described in Objective 2, both arms) will include these same patient-level measures to assess any changes that may mediate or moderate intervention impact (Appendices 2B & 2C). Participants will be compensated 200 KES for completion of each survey.

**Facility assessment form** (Appendix 2D) will be completed at the beginning, mid-point and end of study implementation to assess average resource level, annual PMTCT volume, and PMTCT provider-patient ratios.

**Provider surveys:** At baseline and again at the end of the study period, providers in both arms will be asked to complete a short survey (Appendix 2E) assessing provider role/ department, level of experience, knowledge and motivation regarding current PMTCT guidelines, and barriers and facilitators to provision of complete PMTCT services. We estimate n=5 providers per site to complete the survey for a total of n=60 providers (n=30 intervention, n=30 control). Prior to completing the survey, providers will complete an informed consent (Appendix 2C). Providers will be compensated 500 KES for completion of each survey.

**Supportive Supervision Visits** will occur monthly at all sites. During these visits, Site Coordinators will provide technical assistance and retraining, review study materials (informed consent forms, surveys), and review data for completeness and accuracy. The monthly frequency of site visits approximates programmatic HITSystem 1.0 implementation support in Kenya.

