**Statistical analyses for objective 1 (complete retention).** Data from women who have a documented reason for incomplete care at the study hospital (e.g. transfer facility, pregnancy loss, maternal death) will not be included in analyses. To demonstrate the efficacy of HITSytem 2.1 versus SOC, we will test for differences between arms by modeling complete PMTCT as a function of study arm and selected covariates (e.g., age, partner support, depression) using logistic mixed models with a random site intercept (to adjust for clustering). In post hoc analyses we will explore patient and facility-level characteristics as potential moderators of the effect of HITSytem 2.1, and examine changes in key individual level factors (disclosure status, partner status, depression, partner support) at the midpoint (delivery) and again at the end (6m postpartum). To assess mediating factors, we will compute average levels of provider knowledge and motivation for each site at baseline and end of study. These knowledge and motivation scores, as well as patient knowledge and motivation levels, will be compared pre-post intervention and between study arms to assess change within and between sites. In addition, provider and patient knowledge and motivation will be examined as predictors of PMTCT completion using logistic regression.

[figure not shown]

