**Demografia ya mama:**

1. Tarehe ya kuzaliwa kwa mama: \_\_\_\_\_
2. Nambari ya simu ya mama: \_\_\_\_\_
3. Maelezo ya jinsi mama anaweza kufikiwa:  
\_\_\_\_\_
4. Tarehe ya kwanza ya ujisajili katika huduma za PMTCT: \_\_\_\_\_
5. Makadirio ya tarehe ya kujifungua: \_\_\_\_\_
6. Tarehe uliyo anzishwa huduma za HAART: \_\_\_\_\_
7. Kiwango chako cha juu zaidi cha elimu ni?
  - a. Sina elimu (no formal education)
  - b. Sikumaliza shule ya msingi
  - c. Nilihitimu shule ya msingi
  - d. Sikumaliza sekondari
  - e. Nilihitimu sekondari
  - f. Sikumaliza chuo kikuu
  - g. Nilihitimu chuo kikuu
8. Ni nani umemfahamisha kuhusu hali yako ya VVU?
  - a. Hakuna
  - b. Mchumba/Mume
  - c. Mmoja au zaidi katika familia
  - d. Rafiki/Marafiki
  - e. Mzazi/Wazazi
9. Je, wewe hufikiaje simu ya rununu?
  - a. Nina yangu mwenyewe
  - b. Natumia na mtu anayefahamu hali yangu ya VVU
  - c. Natumia na mtu asiye fahamu hali yangu ya VVU
  - d. Mimi huomba mtu simu ninapohitaji
  - e. Sina njia ya mawasiliano ya simu ya rununu
10. Je, hukuchukua mda gani kufika hospitalini (Dakika) \_\_\_\_\_
11. Gharama za kwenda hospitalini (kuenda na kurudi, KES) \_\_\_\_\_
12. Je, hali yako ya uhusiano ikoje?
  - a. Sijaoa
  - b. Nimeolewa
  - c. Sijaoa lakini niko katika uhusiano
  - d. Nimeachana na mchumba/mume (separated)
  - e. Nimepewa talaka (Divorced)
  - f. Ni Mjane
  - g. Ingingine, fafana \_\_\_\_\_
13. Je, hali yako ya maisha ikoje?
  - a. Sina mpenzi kwa hivi
  - b. Ninaishi kando na mchumba/mume
  - c. Ninaishi na mchumba/mume
14. Una watoto wangapi?
  - a. Uliowazaa mwenyewe \_\_\_\_\_

b. Waliozaliwa na mwingine \_\_\_\_\_

15. Je, umewahi kupata huduma za PMTCT/EID mbeleni? .....Ndio/Hapana

Usaidizi toka kwa mpenzi, na maamuzi kuhusu fedha

16. Je, hali ya VVU ya mchumba wako ikoje?

- a. Ana VVU
- b. Hana VVU
- c. Sijui
- d. Sina mpenzi kwa sasa

17. Je, mpenzi wako alichukulia vipi habari za ujauzito wako?

- a. Alikuwa na raha
- b. Alikua vugu vugu (Neutral)
- c. Hakuwa na raha
- d. Sijui
- e. Sina mpenzi kwa sasa

18. Kwa kawaida, ni nani hufanya uamuzi wa matumizi ya pesa katika boma yako?

- a. Mchumba wangu, kila mara
- b. Mchumba wangu zaidi kuniliko
- c. Sote, kwa usawa
- d. Mimi, mara nyingi kuliko mwenzi wangu
- e. Mimi, kila mara
- f. Sina mpenzi kwa sasa

19. Mapato yako ya wastani katika boma lako kila wiki ni?

- a. Chini ya 500 KES
- b. 500-750 KES
- c. 750-1,000 KES
- d. 1,000-2,500 KES
- e. Zaidi ya 2,500 KES

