**Hali ya Mshirika na Udhihirisho**

1. Hali yako ya uhusiano ni gani?
  - a. Sijaoa
  - b. Nimeolewa
  - c. Sijaoa lakini katika uhusiano
  - d. Nimeachana na mchumba/mume (separated)
  - e. Nimepewa talaka (Divorced)
  - f. Mjane
  - g. Inge, fafaua \_\_\_\_\_
2. Hali yako ya kuishi?
  - a. Sina mwenzi wa uhusiano kwa sasa
  - b. Ninaishi mbali na mpenzi wangu
  - c. Naishi pamoja na mpenzi wangu wa sasa.
3. Je, umemfahamisha nani kuhusu hali yako ya VVU? Chagua majibu yote yanayofaa...
  - a. Hakuna
  - b. Mshiriki/Mchumba/Mume
  - c. Mmoja au zaidi katika familia
  - d. Rafiki/Marafiki
  - e. Mzazi/Wazazi
4. Je, hali ya virusi ya mpenzi wako ikoje?
  - i. Yuko na VVU
  - j. Hana VVU
  - k. Sijui
  - l. Sina mpenzi kwa sasa
5. Je, mpenzi wako wa sasa, ndiye baba wa mtoto wako mchanga?.....Ndio/La
6. Kwa kawaida, ni nani hufanya uamuzi kuhusu utumizi wa pesa katika boma lako?
  - m. Mchumba wangu- kila wakati
  - n. Mchumba wangu- zaidi kuniliko
  - o. Sote, kwa usawa
  - p. Mimi, mara nyingi kuliko mpenzi wangu
  - q. Mimi, kila mara
  - r. Sina mchumba kwa sasa
7. Mapato ya wastani kila wiki, katika boma lako ni?
  - k. Chini ya 500 KES
  - l. 500-750 KES
  - m. 750-1,000 KES
  - n. 1,000-2,500 KES
  - o. Zaidi ya 2,500 KES
8. Nina wasiwasi kwamba sitakuwa na pesa za kutosha kunifikisha hospitalini kwa huduma yangu, au ya mtoto wangu.
  - a. Nakubaliana kabisa
  - b. Nakubali
  - c. Sikubali
  - d. Sikubaliani kabisa

Usaidizi kutoka kwa Mpenzi (Kujazwa wakati wa upimaji kiwango cha virusi wa Miezi 6)

9. Ni kwa kiwango gani mpenzi wako amekusaidia toka ujifungue, kwa njia zifuatazo:

|  | Kamwe | Mara chache | Wakati mwingine | Kila wakati |
|--|-------|-------------|-----------------|-------------|
| 9a. Kuhudhuria miadi ya matibabu ya mtoto wako                 |       |             |                 |             |
| 9b. Kutoa pesa za usafiri kwenda hospitalini                   |       |             |                 |             |
| 9c. Kukupa ushauri kuhusu lishe na usafi wa mtoto              |       |             |                 |             |
| 9d. Kukusaidia na majukumu ya nyumba ili uweze kupumzika       |       |             |                 |             |
| 9e. Kunikumbusha kumpa mtoto dawa.                             |       |             |                 |             |
| 9f. Kuinikumbusha kumeza dawa zangu.                           |       |             |                 |             |

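### The HIV disclosure item carries a multiple-answer instruction on only three of the nine patient forms, so measured change in disclosure may partly reflect form wording

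*Combined protocol and SAP*

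**What the plan says.** Under Procedures and Data Management, the paragraph on participant surveys lists HIV disclosure among the patient-level data collected at enrolment. It says that the repeat surveys after delivery and at 6 months "will include these same patient-level measures to assess any changes that may mediate or moderate intervention impact". Under Objective 1 specific methods, the statistical analysis paragraph says that post hoc analyses will "examine changes in key individual level factors (disclosure status, partner status, depression, partner support" at delivery and again at 6 months postpartum. Disclosure status is the first factor named.

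The item is number 8 in Appendix IIA (enrolment), number 7 in Appendix IIB (delivery) and number 3 in Appendix IIC (6 months). In English it asks "Who have you disclosed your HIV status to" and offers five options: no one, partner or husband, family, friends, parent. The English delivery form adds "Select all that apply". The English enrolment and 6-month forms do not. The Swahili enrolment item, "Ni nani umemfahamisha kuhusu hali yako ya VVU", has no instruction, while the Swahili delivery and 6-month items both add "Chagua majibu yote yanayofaa". The Luo item has no instruction at any of the three surveys.

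The plan gives no coding rule for disclosure status. It does not say whether the variable means disclosure to anyone, disclosure to the partner, or the number of confidants.

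**The concern.** A change analysis needs the same question, answered under the same rule, at each visit. The options are not mutually exclusive: a woman may have told her husband, a sister and a parent. If the interviewer takes one answer where no instruction is printed and several where it is, the record changes when the woman's situation has not. On the English and Swahili forms the instruction changes between enrolment and delivery, which is the first comparison the plan makes.

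At stake is the description of change in disclosure, and any use of disclosure as a mediator or moderator. Disclosure to a specific person, such as the partner, and a count of confidants are exposed. Whether she has told anyone at all is not, because a woman with at least one confidant gives an answer other than no one under either format.

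**Working it through.** The plan states no figure to reproduce. The check is a comparison of the printed item across three surveys and three languages, followed by an illustration.

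**Is a multiple-answer instruction printed?**

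| Form language | Enrolment (IIA item 8) | Delivery (IIB item 7) | 6 months (IIC item 3) |
|---|---|---|---|
| English | No | Yes | No |
| Swahili | No | Yes | Yes |
| Luo | No | No | No |

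The instruction appears on 1 + 2 + 0 = 3 of 9 forms, and no two languages share a pattern. The five options are the same in substance on all nine.

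**What follows if the wording affects recording**

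- English: an apparent rise at delivery that reverses at 6 months.
- Swahili: an apparent rise at delivery that persists.
- Luo: no format-induced change over time, but a format difference from English and Swahili at delivery, and from Swahili at 6 months.

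**Illustrative size.** Both inputs are assumptions; neither is in the documents.

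- True partner disclosure is constant at p = 60%.
- Among these women, a share s have only another confidant recorded when no instruction is printed.
- Where the instruction is printed, the partner is always recorded.

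Recorded partner disclosure is p(1 − s) without the instruction and p with it. On the English and Swahili forms, the spurious enrolment-to-delivery change is p − p(1 − s) = p × s.

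| s | Calculation | Spurious change (percentage points) |
|---|---|---|
| 0% | 60% × 0 | 0 |
| 10% | 60% × 0.10 | 6 |
| 20% | 60% × 0.20 | 12 |
| 30% | 60% × 0.30 | 18 |

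The documents do not fix s, and s = 0 is a live possibility. Under an anyone/no-one coding the spurious change is zero for every s, because a woman who has told someone is counted as having disclosed whichever confidant is recorded.

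**The case against.** The strongest reply is that silence on a form is not a single-answer rule. Where the tools want one answer they can say so: the viral load result items in the 6-month survey and the delivery-support item in the delivery survey both do. The disclosure options plainly overlap, and one trained mentor mother per hospital conducts the surveys on paper, with monthly supervisory review. She may record the item in the same way at all three visits. This stands, and it is why the size may be zero. It does not remove the inconsistency, because no rule for this item is given and the printed wording is the only guidance that the documents show.

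A second reply is that the consequences are limited. That also stands. The analysis is post hoc, both arms use the same forms, pairs are matched within region, and neither primary outcome uses the item. A format shift should largely cancel between arms.

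A reader might infer three stronger things that the documents do not support:

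- **That measured change is in part an artefact, as an established fact.** No form restricts the answer to one option, so this is a possibility only.
- **That form language follows region, so that the distortion follows geography.** The documents say that the patient forms exist in three languages, but not which language is used at which site or by how many women. If Luo forms were used throughout Siaya (4 of the 6 pairs), no format-induced change over time would arise there.
- **That a single figure can be put on the distortion.** Nothing in the documents supports one value; only a range under stated assumptions is defensible.

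**Conclusion.** The point holds as a minor one. The forms do not meet the plan's own statement that the same measures are repeated: the instruction is on three of nine forms, in a different pattern in each language, for a factor whose change the plan names for analysis. Change over time and cross-language comparisons of disclosure may partly reflect this.

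The range of 0 to 18 percentage points for partner disclosure rests on an assumed constant 60% and on an assumed 0 to 30% of these women having only another confidant recorded where no instruction is printed. The underlying gap is that disclosure status is not defined. If it means disclosure to anyone, the problem largely disappears. If it means disclosure to the partner or a count of confidants, it does not.

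**What to change.** **Remaining surveys.** Print one identical select-all instruction on Appendix IIA item 8, Appendix IIB item 7 and Appendix IIC item 3 in English, Swahili and Luo, and brief the interviewers. Record the form language and form version with each response.

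**Forms already completed.** First tabulate multiple marks on this item by visit and form language. If they are common where no instruction is printed, the problem is small.

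**Analysis.** Define the variable before analysis. Base the change analysis on disclosure to anyone (yes/no), which either format captures. Analyse change in partner disclosure only as a sensitivity analysis, stratified by form language and form version. Restricting partner disclosure to forms that carry the instruction is not a good alternative: it would discard every existing enrolment form, and so the baseline, together with every existing Luo form.

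**Cost.** One line of text on six forms, a short briefing, one tabulation and one analysis rule. Some detail is lost for women already surveyed. Because enrolment is under way and two sites have already stopped enrolling, the edit creates a wording break within a visit, which the form-version stratification handles.
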